6.3.4 Ad-hoc Safety Unbinding

CSL's Global Clinical Safety and Pharmacovigilance (GCSP) personnel may, on an ad-hoc basis, unblind the randomization code directly in the IRT at any time during the study, because of a safety concern. The purpose of the unblinded data review is to determine if there is a risk to subject safety that would require further action either for the individual management of a study subject or for the ongoing conduct of the study. The need to unblind a subject or group of subjects may not necessarily arise because of an SAE. The need to unblind on an ad-hoc basis will be determined by CSL's GCSP senior leadership.

7 Contraindications, Permitted Therapies and Prohibited Therapies

7.1 Contraindications and Precautions to Further Dosing

There are no contraindications or precautions associated with CSL312 administration.

The administration of investigational product (CSL312 or placebo) to any subject not meeting the eligibility criteria for this study, or to any patient not enrolled in this study, is prohibited.

7.2 Permitted Therapies

The medications and therapies that are PERMITTED during participation in the study are detailed in Table 5. Note: This list is not intended to be all inclusive.

Table 5 Permitted Medications / Therapies

Medication / Therapy	Dose	Permitted Period of Use
Corticosteroids for acute exacerbations of IPF during study participation	No dose restriction for IPF exacerbation	Treatment duration for acute IPF exacerbation at the investigator's discretion
Antifibrotic therapy (pirfenidone or nintedanib) for disease progression during study participation	According to approved prescribing information	Antifibrotic therapy (pirfenidone or nintedanib) is not permitted during this study as per exclusion criterion #12. However, in the event of disease progression during the study and if, in the investigator's judgment, the subject will benefit from this medication, the subject may receive antifibrotic treatment.
Bronchodilators	According to approved prescribing information	Bronchodilator therapies must be washed out before all PFTs as follows: Short-acting bronchodilators: 8 hours Long-acting bronchodilators: 24 hours
Anticoagulant therapy with LMWH	According to approved prescribing information	Treatment at the investigator's discretion
Low dose aspirin	75 to 100 mg	Treatment at the investigator's discretion
Nonlive influenza virus vaccines and SARS-CoV-2 vaccines	According to prescribing information	Administered at the discretion of the subject's treating physician

IPF = idiopathic pulmonary fibrosis; LMWH = low molecular-weight heparin; PFT = pulmonary function test; SARS-CoV-2 = severe acute respiratory syndrome coronavirus 2.

7.3 Prohibited Therapies

The medications and therapies that are NOT PERMITTED during participation in the study are detailed in Table 6. Note: This list is not intended to be all inclusive.

Table 6 Prohibited Medications / Therapies

Prohibited Medication / Therapy	Prohibited Period of Use
Cytotoxic, immunosuppressive, or cytokine-modulating medication (ie, cyclophosphamide, cyclosporine, methotrexate, etanercept, TNF inhibitors, iloprost, tacrolimus, mycophenolate mofetil)	Within 28 days before randomization (at any time, for any duration, and for any reason) or during the 14-week Treatment and Observation Period
Antifibrotic therapy (nintedanib and pirfenidone)	Within 28 days before randomization and during the 14-week Treatment and Observation Period up to and including the End of Treatment Visit (Day 92) unless administered at the investigator's discretion for disease progression
Anticoagulant therapy other than LMWH	Within 28 days before randomization and during the 14-week Treatment and Observation Period up to and including the End of Treatment Visit (Day 92)
Any investigational therapy other than investigational product	Within 28 days before randomization, or 5 drug half-lives before randomization, whichever is longer During the 14-week Treatment and Observation Period During the 90 days after the last administration of investigational product
Lung transplantation	Planned to occur during study participation

LMWH = low molecular-weight heparin; TNF = tumor necrosis factor.

Subjects should not be enrolled into the study if they receive any prohibited therapy.

If administration of any prohibited therapy becomes necessary during the study for medical reasons, the subject may be withdrawn from further study participation.

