IPF is one of the most common forms of idiopathic interstitial lung disease (ILD) [Kim et al, 2015] and several genetic and environmental risk factors for the disease have been identified. These include male sex, older age, cigarette smoking, environmental exposures such as metal and wood dusts, gastroesophageal reflux disease (GERD), chronic viral infections such as Epstein-Barr virus and hepatitis C, and a family history of ILD [Raghu et al, 2011; Raghu et al, 2018; Sgalla et al, 2018].

Patients with IPF typically present with nonspecific symptoms of exertional dyspnea with or without dry cough. On physical examination, fine, high-pitched bibasilar inspiratory crackles are usually heard, and digital clubbing is present in approximately 30% of patients [Richeldi et al, 2017; Raghu et al, 2018]. The natural history of IPF is highly variable and the course of disease in an individual patient is difficult to predict [Kim et al, 2015]. For some patients, disease progress occurs relatively slowly; others have a rapid decline in lung function leading to death; and a portion of patients suffer a stepwise loss of lung function with periods of relative stability [Kim et al, 2015]. Progression of IPF is characterized by a decline in lung function, worsening symptoms of dyspnea and cough, and deterioration in quality of life [Quinn et al, 2019]. For patients with IPF, acute exacerbations in respiratory function usually result in hospitalization and are associated with high mortality [Collard et al, 2016]. The evidence suggests that up to 46% of deaths in patients with IPF are preceded by an acute exacerbation, with a median survival of approximately 3 to 4 months in these patients [Collard et al, 2016]. Although the course of IPF may be variable, its overall prognosis is poor, with a median survival after diagnosis of only 3 to 4 years in patients who do not receive antifibrotic therapy or undergo lung transplant [Quinn et al, 2019].

Many patients with IPF have comorbid conditions including chronic obstructive pulmonary disease, lung cancer, pulmonary hypertension, obstructive sleep apnea, anxiety, depression, GERD, and ischemic heart disease [Caminati et al, 2019; Raghu et al, 2015a]. Comorbid conditions may affect the disease course in patients with IPF [Raghu et al, 2011], although in most of these patients the cause of death is IPF itself (ie, respiratory failure) [Kim et al, 2015].

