4.3 Discontinuation of Study Treatment and Subject Withdrawal

4.3.1 Discontinuation of Study Treatment

Subjects may discontinue study treatment with investigational product at any time at their own request, or at the discretion of the investigator or CSL for safety, behavioral, or administrative reasons.

Subjects who discontinue treatment with investigational product but remain in the study, will be asked to complete additional follow-up assessments or allow data collection as detailed in the [Schedule of Assessments](#). If a subject discontinues investigational product and declines further study procedures / visit participation, the subject will be withdrawn from the study, and attempts will be made to complete and document the Withdrawal Visit assessments. Refer to Section 4.3.2 and Section 4.3.3 for details on handling subject withdrawals.

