5.3 Treatment for Acute Exacerbation or Disease Progression

At each study visit, subjects will be evaluated for symptoms of acute IPF as defined in [Section 8.1.2](#).

If a subject experiences an acute IPF exacerbation or disease progression, medications or other therapy, including but not limited to antifibrotic agents (nintedanib or pirfenidone), may be administered at the investigator's discretion, at any time during the study.

6 Allocation to Treatment

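### Section 5.3 contradicts Tables 5 and 6 on therapy for acute exacerbation, and Section 7.3 allows study withdrawal after a prohibited therapy without securing collection of new events

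*Protocol*

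**What the plan says.** Protocol Section 5.3 sets a broad rule. "If a subject experiences an acute IPF exacerbation or disease progression, medications or other therapy, including but not limited to antifibrotic agents" "may be administered at the investigator's discretion, at any time during the study". It has two triggers, an open list of therapies and no time limit.

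Table 5 (Section 7.2) lists corticosteroids for acute exacerbations. For antifibrotics it first restates the ban in exclusion criterion 12, then lifts it "in the event of disease progression during the study and if, in the investigator's judgment, the subject will benefit from this medication". Exacerbation is not named there. Table 6 (Section 7.3) bans antifibrotics up to the "End of Treatment Visit (Day 92) unless administered at the investigator's discretion for disease progression". Table 6 also bans cytotoxic, immunosuppressive and cytokine-modulating drugs during the 14 weeks, and anticoagulants other than low molecular-weight heparin (LMWH) to Day 92. Neither of those bans has an exception for events during the study. Exclusion criterion 12 (Section 4.1.2) bans antifibrotics to Day 92 with no exception in its own text.

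Section 7.3 closes with the consequence: "If administration of any prohibited therapy becomes necessary during the study for medical reasons, the subject may be withdrawn from further study participation". Section 4.3.1 provides another route: "Subjects who discontinue treatment with investigational product but remain in the study, will be asked to complete additional follow-up assessments". Section 7.3 does not refer to it.

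**The concern.** There are two linked problems.

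First, a site treating an acute exacerbation can follow Section 5.3 and, by the same act, give a therapy that Table 6 prohibits. Two sites with the same patient could classify and handle the case differently.

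Second, the stated consequence of a prohibited therapy is possible exit from the study, not only from product. The subjects exposed to that sentence are those who had a medical reason for the therapy, such as an exacerbation or a thromboembolic event. The primary endpoint is the number and proportion of subjects with treatment-emergent adverse events (TEAEs), including SAEs and adverse events of special interest (AESIs). If CSL312 alters the frequency of the triggering events in either direction, loss of later data could differ between arms. Whether a Day 92 FVC exists would also depend partly on how the site applied Section 7.3.

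**Working it through.** **Step 1: the rules side by side.**

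| Situation up to Day 92 | Section 5.3 | Table 5 | Table 6 | Result |
|---|---|---|---|---|
| Antifibrotic for disease progression | allowed | allowed | excepted from ban | consistent, but criterion 12 has no exception |
| Antifibrotic for acute exacerbation | allowed | outside the exception | prohibited | conflict |
| Corticosteroid for acute exacerbation | allowed | allowed | not listed | consistent |
| Immunosuppressant for either trigger | allowed by the open list | not listed | prohibited, no exception | conflict |
| Non-LMWH anticoagulant after a thromboembolic event | not covered | only LMWH listed | prohibited | no contradiction, but the withdrawal sentence applies |

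Exacerbation cannot simply be read into progression. Section 5.3 joins the two with 'or', and Table 5 gives them separate rows.

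**Step 2: what continues after withdrawal.**

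- Sections 4.3.3 and 8.5.7 and Schedule of Assessments note C call for end-of-treatment assessments, and 4.3.3 asks for every effort on relevant safety assessments.
- Sections 9.5, 9.6.1 and 9.6.3 follow events that have already begun. Section 9.6.3 covers subjects no longer participating.
- After the end-of-treatment visit, 9.6.3 requires reporting of SAEs judged causally related, and keeps them out of the eCRF.
- Section 9.4 runs adverse event observation to the follow-up call, but no text says a withdrawn subject receives that call.
- The public-records check in 4.3.3 is written for subjects who also withdraw consent for disclosure.

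So events already started are covered. New events after the early-withdrawal visit are not assured.

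**Step 3: the window exposed.** Days left = 92 − d and 154 − d. The withdrawal days below are dosing days chosen for illustration.

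| Withdrawal day d | Days to Day 92 | Days to Day 154 call |
|---|---|---|
| 8 | 84 | 146 |
| 36 | 56 | 118 |
| 64 | 28 | 90 |

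SAP Section 11.2 counts TEAEs only through the Treatment and Observation Period, which SAP Section 8.4 ends at Day 92. The Day 92 column is therefore what matters for the TEAE tables. The Day 154 column matters for listings and for the overall safety record.

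**Step 4: size per subject.** The plan's own figure reproduces: 70/(1 − 0.12) = 79.5, rounded up to 80, or 40 per arm. One subject whose new event is missed changes an arm's proportion by 1/40 = 2.5 percentage points. The documents give no rate of exacerbation, of prohibited-therapy use or of withdrawal under 7.3, so the number of such subjects cannot be computed. The dropout allowance of 40 − 35 = 5 per arm is not broken down by cause.

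**The case against.** The strongest reply is that this is a narrow drafting conflict with safeguards around it. Much of that reply stands.

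- A reader might infer three competing rules. There are two: Sections 7.2 and 7.3 agree on antifibrotics, and 5.3 differs from both.
- A reader might infer that any rescued subject can be withdrawn under 7.3. The sentence reaches only prohibited therapies. Corticosteroids for exacerbation, antifibrotics for progression, and LMWH are permitted.
- Withdrawal is permissive. For a confirmed thromboembolic event, Section 3.9.1 pauses dosing pending assessment and does not order withdrawal.
- A reader might take the protocol's survival figure after exacerbation, "with a median survival of approximately 3 to 4 months in these patients", and compute a share of deaths missed. The documents do not support that. The figure gives a chance of dying, not of a death going unrecorded. Section 1.1 says exacerbations usually lead to hospitalization, and a stay of at least 24 hours is an SAE criterion in 9.1.2. A death from that event would then normally be the outcome of an SAE already being followed. Such a subject is also already counted as having a TEAE and an SAE.
- There is no primary hypothesis, safety is summarized descriptively, and FVC is exploratory. No differential loss between arms has been shown.

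The reply does not remove two things. The note that Table 5 is not exhaustive cannot override an explicit ban in Table 6. And following events already under way does not collect new ones, such as a later AESI or an SAE with a different cause.

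**Conclusion.** The point holds in two parts.

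1. Section 5.3 contradicts Tables 5 and 6 on antifibrotics for acute exacerbation and on immunosuppressants for either trigger. Exclusion criterion 12 does not carry the exception that both tables make. These passages must be reconciled; this review takes no view on which therapies should be allowed.
2. Section 7.3 permits study withdrawal after a prohibited therapy without reference to Section 4.3.1. Collection of new events to Day 92, and the Day 154 call, is then not assured.

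The size is 2.5 percentage points per missed subject, assuming about 40 treated per arm, with an unknown number of subjects. The risk is one of selective loss, because the exposed subjects are those with exacerbations or AESIs. It bears mainly on individual event categories and AESIs rather than on the proportion with any TEAE. It also bears on FVC, since SAP Section 13.2.1 plans no imputation. The conclusion rests on the text alone. It does not assume that sites would usually choose withdrawal, or that loss would differ by arm. The change should be made because the rule as written touches the primary endpoint and is cheap to correct.

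**What to change.** 1. Reconcile Section 5.3, Table 5, Table 6 and exclusion criterion 12 so that each combination of therapy and trigger has one status. Which therapies are acceptable is for the sponsor's clinicians.
2. Amend the closing sentence of Section 7.3 so that use of a prohibited therapy does not by itself end study data collection. Any stop of product would follow Section 4.3.1. The scheduled visits, Day 92 assessments and Day 154 call would continue unless the subject declines or is withdrawn for safety or wellbeing under Section 4.3.2. In those cases, collection of new adverse events and vital status would continue as far as consent allows.

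The cost is a protocol wording amendment and a few visits and calls that are already scheduled. No new procedure is needed.

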7.4 Lifestyle Restrictions

Female subjects of childbearing potential or male subjects must use a medically reliable form of contraception until 90 days after the last administration of the investigational product.

Acceptable methods of contraception are:

- Abstinence, where abstinence is the preferred and usual lifestyle of the subject, including refraining from heterosexual intercourse during the entire period of risk associated with the investigational product. Periodic abstinence (calendar, symptothermal, postovulation methods), withdrawal (coitus interruptus), spermicides only, and lactational amenorrhea method are not acceptable definitions of abstinence.
- Hormonal methods associated with inhibition of ovulation. Acceptable hormonal methods include: oral contraceptives, contraceptive medication patch, contraceptive medication injection, estrogen / progestin vaginal ring, or contraceptive medication implant.
- Use of intrauterine device (placed > 3 months before providing informed consent).
- Bilateral tubal occlusion of female subjects (\geq 3 months before providing informed consent).
- Vasectomy of male subjects (\geq 3 months before providing informed consent).

8 Study Procedures and Visit Schedule

8.1 Clinical Procedures

The timing and frequency of the clinical procedures described in the following sections are detailed in the [Schedule of Assessments](#). More frequent assessments may be performed, if clinically indicated, at the discretion of the investigator. Refer to the provided study manual for detailed instructions on how the assessments should be performed.

8.1.1 Demographics and Safety Assessments

Subject demographics and safety assessments to be conducted during this study are provided in Table 7. Clinical laboratory assessments are to be performed at the time points indicated in the [Schedule of Assessments](#).

Table 7 Study Procedures: Demographics and Safety Assessments

Assessment	Description
Demographics	
 • Year of birth • Sex • Age • Race and ethnicity (where permitted)
Medical history	
 • Relevant medical history • Diagnosis and disease status • Contraception method (if relevant) • Previous (within 6 months before Screening) and concomitant medications and therapies
Pregnancy test (local laboratory)	A serum test for β -hCG will be performed for all female subjects of childbearing potential to rule out pregnancy at Screening. At all other study visits, a urine pregnancy test will be performed. If the results from the urine pregnancy test are inconclusive, the site will perform a serum pregnancy test.
Physical examination	As per the site's standard procedure, including assessment of unilateral pain and / or swelling of the lower extremities for the purposes of screening for DVTs.
12-lead ECG (Performed and analyzed locally)	
 • Heart rate • PR interval • QRS duration • Interpretation (investigator's overall interpretation) • QT interval • QTcB interval • QTcF interval
PFTs	
 • Spirometry including FVC and FEV₁ • DL_{CO}
AEs	
 • Evaluation of all AEs (eg, causality / relatedness, severity, seriousness) • AESIs: 
 ○ Abnormal bleeding events ○ TEEs ○ Severe hypersensitivity including anaphylaxis 
The description of AEs and reporting requirements are detailed in Section 9.

Vital signs	
 • Blood pressure (systolic and diastolic) • Respiratory rate • Heart rate • Body temperature • Height (Screening only) • Weight and BMI
Urinalysis (dipstick) (central laboratory)	
 • Specific gravity • pH • Nitrite • Ketones • Protein • Glucose • Occult blood • Leukocyte esterase • Erythrocytes • Bilirubin • Urobilinogen

Assessment	Description
Hematology (central laboratory)	
 • Hematocrit • Platelets • Erythrocytes (RBC count) • RBC indices (MCHC, MCH, MCV, RDW) • Hemoglobin • Reticulocytes • Leukocytes (WBC count) • Differential (percentage and absolute): neutrophils, neutrophil band forms, lymphocytes, monocytes, eosinophils, basophils
Biochemistry (central laboratory)	
 • Sodium • Potassium • Chloride • Bicarbonate • Calcium • BUN • Urea • Creatinine • Glucose • Protein – total • Albumin • Alkaline phosphatase • ALT • AST • LDH • GGT • Bilirubin – total • Direct bilirubin • Magnesium • Phosphate • hs-CRP • Cholesterol – total • Triglycerides • HDL cholesterol • LDL cholesterol • Urate (Uric Acid) • CK / CPK
Coagulation for safety assessments (local laboratory)	
 • INR 
D-dimer

Coagulation for biomarker assessments (central laboratory)	
 • aPTT • pF1+2 • D-dimer • PT and INR • Fibrinogen (Clauss assay)
Immunogenicity (ADAs) (central laboratory)	Plasma analyzed for the presence of binding antibodies (neutralizing and non-neutralizing) specific to FXIIa antagonist monoclonal antibody (anti-CSL312).

β -hCG = beta-human chorionic gonadotropin; ADA = antidrug antibody; AE = adverse event; AESI = adverse event of special interest; ALT = alanine aminotransferase; aPTT = activated partial thromboplastin time; AST = aspartate aminotransferase; BMI = body mass index; BUN = blood urea nitrogen; CK = creatinine kinase; CPK = creatinine phosphokinase; DL_{CO} = diffusing capacity of the lungs for carbon monoxide; DVT = deep vein thrombosis; ECG = electrocardiogram; FEV₁ = Forced expiratory volume in 1 second; FVC = forced vital capacity; FXIIa = activated coagulation factor XII; GGT = gamma glutamyl transferase; HDL = high-density lipoprotein; hs-CRP = high-sensitivity C-reactive protein; INR = international normalized ratio; LDH = lactate dehydrogenase; LDL = low-density lipoprotein; MCH = mean corpuscular hemoglobin; MCHC = mean corpuscular hemoglobin concentration; MCV = mean corpuscular volume; pF1+2= prothrombin fragment; PFT = pulmonary function tests; PT = prothrombin time; QTcB = Bazett's correction formula; QTcF = Fridericia's correction formula; RBC = red blood cell; RDW = red cell (erythrocyte) distribution width; TEE = thromboembolic event; WBC = white blood cell.

Results of laboratory tests (hematology, coagulation, biochemistry, and urinalysis) completed at the central laboratory should be signed and dated and retained at the study site as source data. The investigator should make an evaluation of the available safety-assessment results with regard to clinically relevant abnormalities. Refer to [Section 9](#) for information on how AEs based on laboratory tests should be assessed and reported.

Laboratory Parameters

Details related to the collection, preparation, storage, and transfer of blood and urine samples for laboratory assessments will be provided in the Laboratory Manual.

Refer to [Section 9.1.1](#) for assessment of abnormal laboratory values. Tests resulting in abnormal laboratory values during the study period that have been classified by the investigator as clinically significant should be followed up after receiving the laboratory report, and may include an unscheduled repeat safety sampling at the discretion of the investigator.

Vital Signs

Blood pressure and heart rate will be measured with the subject in a supine or seated position after resting for 5 (\pm 3) minutes. Body temperature will be measured either sublingually or tympanically, and the method of measurement should be consistent throughout the study for a given subject.

